6.1 Study treatment

The investigational treatments for this study are asciminib (40 mg BID) and bosutinib (500 mg QD). Novartis will supply asciminib to the investigational site as 20 mg and 40 mg tablets. Bosutinib will be supplied to the investigational site as 100 mg and 500 mg tablets.

6.1.1 Dosing regimen

Asciminib

Asciminib 20 or 40 mg strength tablets will be administered orally twice-daily (BID), without food. Asciminib tablets should be ingested as follows:

- Asciminib should be administered in the fasted state: avoid food for at least 2 hours before the dose is taken and for at least 1 hour after the dose is taken. Water is permitted during this period.
- Asciminib should be taken with approximately 8 ounces (240 mL) of water.
- Asciminib should be swallowed whole and not chewed or crushed.
- If vomiting occurs within the first hour after taking the drug, re-dosing is allowed before the next scheduled dose

- If the patient does not take asciminib within 6 hours after the approximate time of the usual dosing time, that dose should be skipped and treatment should continue with the next daily dose at the prescribed level

Bosutinib

Bosutinib 500 mg or 100 mg tablets will be administered orally once daily (QD) with food. If a dose is missed beyond 12 hours, the patient should skip the dose and take the usual dose on the following day.

Table 6-1 Dose and treatment schedule

Study treatments	Pharmaceutical form and route of administration	Dose	Frequency and/or Regimen	Fasting Condition
Asciminib	Tablet for oral use	20 mg ^a	Twice-daily	Fasting
Asciminib	Tablet for oral use	40 mg	Twice-daily	Fasting
Bosutinib	Tablet for oral use	100 mg ^b	Once-daily	Non-fasting
Bosutinib	Tablet for oral use	500 mg	Once-daily	Non-fasting

^a 20 mg tablets will be dispensed to patients in the instance of dose reduction.

^b 100 mg tablets will be dispensed to patients in the instance of dose modifications.

On days when serial blood samples are collected for asciminib PK analysis, patients will be instructed to bring their drug supply to the site, and take the dose in the clinic, under supervision of the site personnel. The exact time for dose administration and meal intake must be recorded in the electronic Case Report Form (eCRF).

All dosages prescribed and dispensed to the patient and all dose changes during the study must be recorded on the Dosage Administration Record eCRF.

6.1.2 Ancillary treatments

Not applicable.

6.1.3 Rescue medication

Not applicable.

6.1.4 Guidelines for continuation of treatment

Not applicable. See [Section 6.3](#).

6.1.5 Treatment duration

There is no fixed duration of treatment planned per patient. The patients are treated in the study up to end of study treatment period defined as up to 96 weeks after the last patient receives the first dose or up to 48 weeks after the last patient has switched to asciminib treatment whichever is longer unless patients have discontinued treatment earlier. Patients may be discontinued from treatment with the study drug at any time due to unacceptable toxicity, disease progression and/or at the discretion of the investigator or the patient.

6.2 Dose escalation guidelines

Dose escalation beyond the standard doses of 40 mg BID for asciminib is not permitted.

Dose escalation above 500 mg QD for bosutinib is permitted in this study. Bosutinib escalation guidelines are as follows:

Consider dose escalation to 600 mg once daily in patients who are currently taking 500 mg daily, did not have Grade 3 or higher adverse events and who:

- Did not reach complete hematological response (CHR) by week 8
- Did not reach complete cytogenetic response (CCyR) by week 12

6.3 Dose modifications

6.3.1 Dose modification and dose delay

For patients who do not tolerate the protocol-specified dosing schedule, dose interruptions and/or reductions are either recommended or mandated in order to allow the patient to continue the study treatment.

These dose modifications are summarized in [Table 6-2](#). The dose reduction indicated as “recommendations” are provided to assist investigators in the event the patient experiences toxicity. However, deviations from “mandatory” dose interruptions and/or reductions are not allowed and mandatory interruptions or reductions must be strictly followed. Re-escalation to asciminib 40 mg BID is permitted if a change in the patient’s individual benefit/risk assessment at the lower dose level is seen. Re-escalation will be allowed only once for any given patient on the asciminib arm per protocol. Permanent treatment discontinuation is mandatory for specific events indicated as such in [Table 6-2](#). Any dose changes must be recorded on the Dosage Administration Record eCRF.

A patient must discontinue treatment with either asciminib or bosutinib if, after treatment is resumed at a lower dose level, the toxicity recurs with the same or worse severity, except for recurrence of cytopenias ([Table 6-2](#)). If a patient requires a dose interruption of > 28 days for each non-hematologic toxicity, then the patient must be discontinued from the study treatment. If a hematologic toxicity (cytopenia Grade 3 or 4) lasts for more than 42 days without recovery to at least a Grade 2, despite TKI interruption and adequate management (including hematopoietic growth factors), then the patient must be discontinued from the study treatment.

Table 6-2 Criteria for dose reduction/interruption and re-initiation of asciminib and bosutinib treatment for adverse drug reactions

[figure not shown]
Dose modifications for both asciminib and bosutinib		
Please note that if a patient requires a dose interruption of > 28 days for each toxicity, then the patient must be discontinued from the study treatment		
Worst toxicity CTCAE Grade 4.03	Asciminib	Bosutinib
Investigations (Hematologic) If a hematologic toxicity (cytopenia Grade 3 or 4) lasts for more than 42 days without recovery to at least a Grade 2, despite TKI interruption and adequate management (including hematopoietic growth factors), then the patient must be discontinued from the study treatment.		
Neutropenia (ANC)		
Grade 1 (ANC < LLN – 1.5 x 10 ⁹ /L)	Recommendation: Maintain dose level	Recommendation: Maintain dose level
Grade 2 (ANC < 1.5 – 1.0 x 10 ⁹ /L)	Recommendation: Maintain dose level	Recommendation: Maintain dose level
Grade 3 (ANC < 1.0 – 0.5 x 10 ⁹ /L)	Mandatory: Hold dose until resolved to ≤ Grade 2 (recheck CBC 2x/week), then: if resolved in ≤ 14 days, then maintain dose level If resolved in > 14 days, then reduce dose ↓ 1 dose level	Mandatory: Hold dose until resolved to ≤ Grade 2 and platelets ≤ Grade 2 (recheck CBC 2x/week), then: if resolved in ≤ 14 days, then maintain dose level If resolved in > 14 days, reduce dose ↓ 1 dose level
Grade 4 (ANC < 0.5 x 10 ⁹ /L)	Mandatory: Hold dose until resolved to ≤ Grade 2, (recheck CBC 2x/week), then: if resolved in ≤ 14 days, then maintain dose level if resolved in > 14 days, then reduce dose ↓ 1 dose level	Mandatory: Hold dose until resolved to ≤ Grade 2 and platelets ≤ Grade 2 (recheck CBC 2x/week), then: if resolved in ≤ 14 days, then maintain dose level if resolved in > 14 days, then reduce dose ↓ 1 dose level
Febrile neutropenia (ANC < 1.0 x 10 ⁹ /L, fever ≥ 38.5°C)	Mandatory: Hold dose until resolved, then reduce dose ↓ 1 dose level	Mandatory: Hold dose until resolved, then reduce dose ↓ 1 dose level
Thrombocytopenia		
Grade 1 (PLT < LLN – 75 X 10 ⁹ /L)	Recommendation: Maintain dose level	Recommendation: Maintain dose level
Grade 2 (PLT < 75 - 50 x 10 ⁹ /L)	Recommendation: Maintain dose level	Recommendation: Maintain dose level

[figure not shown]
Dose modifications for both asciminib and bosutinib		
Please note that if a patient requires a dose interruption of > 28 days for each toxicity, then the patient must be discontinued from the study treatment		
Worst toxicity CTCAE Grade 4.03	Asciminib	Bosutinib
Grade 3 (PLT < 50 - 25 x 10 ⁹ /L)	Mandatory: Hold dose until resolved to ≤ Grade 2 (recheck CBC 2x/week), then: if resolved in ≤ 14 days, then maintain dose level if resolved in > 14 days, then reduce dose ↓ 1 dose level	Mandatory: Hold dose until resolved to ≤ Grade 2 and neutrophils ≤ Grade 2 (recheck CBC 2x/week), then: if resolved in ≤ 14 days, then maintain dose level if resolved in > 14 days, then reduce dose ↓ 1 dose level
Grade 4 (PLT < 25 x 10 ⁹ /L)	Mandatory: Hold dose until resolved to ≤ Grade 2 (recheck CBC 2x/week), then: if resolved in ≤ 14 days, then maintain dose level if resolved in > 14 days, then reduce dose ↓ 1 dose level	Mandatory: Hold dose until resolved to ≤ Grade 2 and neutrophils ≤ Grade 2 (recheck CBC 2x/week), then: if resolved in ≤ 14 days, then maintain dose level if resolved in > 14 days, then reduce dose ↓ 1 dose level
Recurrence of all cytopenias	Recommendation: Hold dose until resolved to ≤ Grade 2, then maintain current dose level.	Recommendation: Hold dose until resolved to ≤ Grade 2, then reduce dose ↓ 1 additional level
Non-hematologic adverse reactions except where further specified in individual sections		
Grade 1	Recommendation: Maintain dose level	Recommendation: Maintain dose level
Grade 2	Recommendation: Hold dose until resolved to ≤ Grade 1, then maintain dose level	Recommendation: Maintain dose level
Grade 3	Mandatory: Hold dose until resolved to ≤ Grade 1, then reduce dose ↓ 1 dose level	Mandatory: Hold dose until resolved to ≤ Grade 1, then reduce dose ↓ 1 dose level, If clinically appropriate, re-escalation of the dose back to baseline dose level (500 mg) should be considered
Grade 4	Mandatory: Permanently discontinue patient from study drug treatment.	Mandatory: Hold dose until resolved to ≤ Grade 1, then reduce dose ↓ 1 dose level; If clinically appropriate, re-escalation of the dose back to baseline dose level (500 mg) should be considered
Investigations (Renal)		
Serum creatinine		
Grade 1 (> ULN - 1.5 x ULN)	Recommendation: Maintain dose level	Recommendation: Maintain dose level
Grade 2 (> 1.5 - 3.0 x ULN)	Recommendation: Hold dose until resolved to ≤ Grade 1 or baseline, then maintain dose level	Recommendation: Hold dose until resolved to ≤ Grade 1 or baseline, then maintain dose level
Grade 3 (> 3.0 - 6.0 x ULN)	Mandatory: Permanently discontinue patient from study drug treatment.	Mandatory: Permanently discontinue patient from study drug treatment.
Grade 4 (> 6.0 x ULN)	Mandatory: Permanently discontinue patient from study drug treatment.	Mandatory: Permanently discontinue patient from study drug treatment.

[figure not shown]
Dose modifications for both asciminib and bosutinib		
Please note that if a patient requires a dose interruption of > 28 days for each toxicity, then the patient must be discontinued from the study treatment		
Worst toxicity CTCAE Grade 4.03	Asciminib	Bosutinib
Investigations (Hepatic)		
Isolated total Bilirubin elevation		
> ULN – 1.5 x ULN	Recommendation: Maintain dose level	Recommendation: Maintain dose level
> 1.5 - 3.0 x ULN	Recommendation: Hold dose. Monitor LFTs ^b weekly, or more frequently if clinically indicated, until resolved to ≤ 1.5 x ULN: if resolved in ≤ 14 days, then maintain dose level if resolved in > 14 days, then reduce dose ↓ 1 dose level	Recommendation: Hold dose. Monitor LFTs ^b weekly, or more frequently if clinically indicated, until resolved to ≤ 1.5 x ULN: if resolved in ≤ 14 days, then maintain dose level if resolved in > 14 days, then reduce dose ↓ 1 dose level
> 3.0 - 10.0 x ULN*	Mandatory: Hold dose. Monitor LFTs ^b weekly, or more frequently if clinically indicated, until resolved to ≤ 1.5 x ULN: if resolved in ≤ 14 days, then reduce dose ↓ 1 dose level if resolved in > 14 days, then discontinue patient from study drug treatment. The patient should be monitored weekly (including LFTs ^b), or more frequently if clinically indicated, until total bilirubin have resolved to baseline or stabilization over 4 weeks.	Mandatory: Hold dose. Monitor LFTs ^b weekly, or more frequently if clinically indicated, until resolved to ≤ 1.5 x ULN: if resolved in ≤ 14 days, then reduce dose ↓ 1 dose level if resolved in > 14 days, then discontinue patient from study drug treatment. The patient should be monitored weekly (including LFTs ^b), or more frequently if clinically indicated, until total bilirubin have resolved to baseline or stabilization over 4 weeks.
> 10.0 x ULN*	Mandatory: Permanently discontinue patient from study drug treatment. The patient should be monitored weekly (including LFTs ^b), or more frequently if clinically indicated, until total bilirubin have resolved to baseline or stabilization over 4 weeks.	Mandatory: Permanently discontinue patient from study drug treatment. The patient should be monitored weekly (including LFTs ^b), or more frequently if clinically indicated, until total bilirubin have resolved to baseline or stabilization over 4 weeks.
Isolated AST or ALT elevation		
> ULN - 3.0 x ULN	Recommendation: Maintain dose level	Recommendation: Maintain dose level
> 3.0 - 5.0 x ULN	Recommendation: Maintain dose level. Repeat LFTs ^b as soon as possible, preferably within 48-72 hours from awareness of the abnormal results; if abnormal lab values are confirmed upon the repeat test, then monitor LFTs ^b weekly, or more frequently if clinically indicated, until resolved to ≤ 3.0 x ULN	Recommendation: Maintain dose level. Repeat LFTs ^b as soon as possible, preferably within 48-72 hours from awareness of the abnormal results; if abnormal lab values are confirmed upon the repeat test, then monitor LFTs ^b weekly, or more frequently if clinically indicated, until resolved to ≤ 3.0 x ULN

[figure not shown]
Dose modifications for both asciminib and bosutinib Please note that if a patient requires a dose interruption of > 28 days for each toxicity, then the patient must be discontinued from the study treatment		
Worst toxicity CTCAE Grade 4.03	Asciminib	Bosutinib
> 5.0 - 10.0 x ULN	Mandatory: Hold dose. Repeat LFTs ^b as soon as possible, preferably within 48-72 hours from awareness of the abnormal results; monitor LFTs ^b weekly, or more frequently if clinically indicated, until resolved to ≤ 3.0 x ULN: Then If resolved in ≤ 14 days, maintain dose level If resolved in > 14 days, reduce dose ↓ 1 dose level	Mandatory: Hold dose. Repeat LFTs ^b as soon as possible, preferably within 48-72 hours from awareness of the abnormal results; monitor LFTs ^b weekly, or more frequently if clinically indicated, until resolved to ≤ 2.5 x ULN: Then Recommendation: If resolved in ≤ 28 days, reduce dose ↓ 1 dose level Recommendation: If resolved in > 28 days, Discontinue patient from study drug treatment
> 10.0 - 20.0 x ULN	Mandatory: Hold dose. Repeat LFTs ^b as soon as possible, preferably within 48-72 hours from awareness of the abnormal results; monitor LFTs ^b weekly, or more frequently if clinically indicated, until resolved to ≤ baseline. Then reduce dose ↓ 1 dose level.	Mandatory: Hold dose. Repeat LFTs ^b as soon as possible, preferably within 48-72 hours from awareness of the abnormal results; monitor LFTs ^b weekly, or more frequently if clinically indicated, until resolved to ≤ 2.5 x ULN. Then Recommendation: If resolved in ≤ 28 days, reduce dose ↓ 1 dose level maintain dose level Recommendation: If resolved in > 28 days, Discontinue patient from study drug treatment.
> 20.0 x ULN	Mandatory: Hold dose. Repeat LFTs ^b as soon as possible, preferably within 48-72 hours from awareness of the abnormal results; monitor LFTs ^b weekly, or more frequently if clinically indicated, until resolved to ≤ 3 x ULN (or ≤ 5 x ULN for patients with baseline value > 3.0 -5.0 x ULN), then resume treatment at reduce dose ↓ 1 dose level. Only 1 dose reduction is allowed; if reoccurs at > 5 x ULN, discontinue patient from study drug treatment.	Mandatory: Hold dose. Repeat LFTs ^b as soon as possible, preferably within 48-72 hours from awareness of the abnormal results; monitor LFTs ^b weekly, or more frequently if clinically indicated, until resolved to ≤ 2.5 x ULN (then Recommendation: If resolved in ≤ 28 days, reduce dose ↓ 1 dose level maintain dose level Recommendation: If resolved in > 28 days, Discontinue patient from study drug treatment

Dose modifications for both asciminib and bosutinib		
Please note that if a patient requires a dose interruption of > 28 days for each toxicity, then the patient must be discontinued from the study treatment		
Worst toxicity CTCAE Grade 4.03	Asciminib	Bosutinib
Combined ^c elevations of AST or ALT and total bilirubin		
For patients with normal baseline ALT and AST and total bilirubin value: AST or ALT >3.0 x ULN combined with total bilirubin >2.0 x ULN without evidence of cholestasis ^d For patients with elevated baseline AST or ALT or total bilirubin value [AST or ALT >2 x baseline AND > 3.0 x ULN]	Mandatory: Permanently discontinue patient from study drug treatment. Repeat as soon as possible, preferably within 48 hours from awareness of the abnormal results, then with weekly monitoring of LFTs ^b), or more frequently if clinically indicated, until AST, ALT, or bilirubin have resolved to baseline or stabilization over 4 weeks. Refer to Section 6.3.3.1 for additional follow-up evaluations as applicable.	Mandatory: Permanently discontinue patient from study drug treatment. Repeat as soon as possible, preferably within 48 hours from awareness of the abnormal results, then with weekly monitoring of LFTs ^b), or more frequently if clinically indicated, until AST, ALT, or bilirubin have resolved to baseline or stabilization over 4 weeks. Refer to Section 6.3.3.1 for additional follow-up evaluations as applicable.
Investigation (metabolic)		
Asymptomatic amylase and/or lipase elevation		
Grade 1 (> ULN - 1.5 x ULN)	Recommendation: Maintain dose level, measure 2x week	Recommendation: Maintain dose level, measure 2x week
Grade 2 (> 1.5 - 2.0 x ULN)	Recommendation: Maintain dose level, measure 2x week	Recommendation: Maintain dose level, measure 2x week
Grade 3 (> 2.0 - 5.0 x ULN)	Mandatory: Hold dose until resolved to Grade ≤ 1 or baseline, then: If resolved in ≤ 7 days, then reduce dose ↓ 1 dose level If resolved in > 7 days, then discontinue treatment and obtain appropriate imaging (i.e., MRI, CT scan or ultrasound).	Mandatory: Hold dose until resolved to Grade ≤ 1 or baseline, then: If resolved in ≤ 7 days, then reduce dose ↓ 1 dose level If resolved in > 7 days, then discontinue treatment and obtain appropriate imaging (i.e., MRI, CT scan or ultrasound).
Grade 4 (> 5.0 x ULN)	Mandatory: Permanently discontinue patient from study drug treatment. Obtain appropriate imaging (i.e., MRI, CT scan or ultrasound).	Mandatory: Permanently discontinue patient from study drug treatment. Obtain appropriate imaging (i.e., MRI, CT scan or ultrasound).

Dose modifications for both asciminib and bosutinib		
Please note that if a patient requires a dose interruption of > 28 days for each toxicity, then the patient must be discontinued from the study treatment		
Worst toxicity CTCAE Grade 4.03	Asciminib	Bosutinib
Vascular disorders		
Hypertension		
CTCAE Grade 3	Mandatory: Hold dose until resolved ≤ Grade 1, then reduce dose ↓ 1 dose level	Mandatory: Hold dose until resolved ≤ Grade 1, then reduce dose ↓ 1 dose level
CTCAE Grade 4	Mandatory: Permanently discontinue patient from study drug treatment.	Mandatory: Permanently discontinue patient from study drug treatment.
Gastro intestinal		
Pancreatitis		
Grade 2 (radiologic findings for pancreatitis as per CTCAE v4.03, for increased enzymes please see table for asymptomatic amylase and/or lipase elevation)	Mandatory: If asymptomatic radiologic pancreatitis, hold treatment until recovery of the radiologic findings. If treatment delay is ≤ 21 days, then reduce dose ↓ 1 dose level. If treatment delay > 21 days, discontinue treatment and keep monitoring with appropriate imaging (i.e., MRI, CT scan or ultrasound).	Mandatory: If asymptomatic radiologic pancreatitis, hold treatment until recovery of the radiologic findings. If treatment delay is ≤ 21 days, then reduce dose ↓ 1 dose level. If treatment delay > 21 days, discontinue treatment and keep monitoring with appropriate imaging (i.e., MRI, CT scan or ultrasound).
Grade ≥ 3	Mandatory: Permanently discontinue patient from study drug treatment. Obtain appropriate imaging (i.e., MRI, CT scan or ultrasound).	Mandatory: Permanently discontinue patient from study drug treatment. Obtain appropriate imaging (i.e., MRI, CT scan or ultrasound).
Diarrhea***		
Grade 1	Recommendation: Maintain dose level but, initiate anti-diarrhea treatment	Recommendation: Maintain dose level but, initiate anti-diarrhea treatment
Grade 2	Recommendation: Hold dose until resolved to ≤ grade 1, then maintain dose level. If diarrhea returns as ≥ grade 2, then hold dose until resolved to ≤ grade 1, then reduce dose ↓ 1 dose level	Recommendation: Hold dose until resolved to ≤ grade 1, then maintain dose level. If diarrhea returns as ≥ grade 2, then hold dose until resolved to ≤ grade 1, then reduce dose ↓ 1 dose level
Grade 3	Recommendation: Hold dose and discontinue patient from study drug treatment	Mandatory: Hold dose until recovery to ≤ grade 1. Recommendation: Bosutinib may then be resumed at ↓ 1 dose level
Grade 4	Mandatory: Permanently discontinue patient from study drug treatment	Mandatory: Hold dose until recovery to ≤ grade 1. Recommendation: Bosutinib may then be resumed at ↓ 1 dose level

Dose modifications for both asciminib and bosutinib		
Please note that if a patient requires a dose interruption of > 28 days for each toxicity, then the patient must be discontinued from the study treatment		
Worst toxicity CTCAE Grade 4.03	Asciminib	Bosutinib
Skin and subcutaneous tissue disorders		
Rash/photosensitivity		
Grade 1	Recommendation: Maintain dose level. Consider to initiate appropriate skin toxicity therapy (such as antihistamines, topical corticosteroids and low-dose systemic corticosteroids)	Recommendation: Maintain dose level. Consider to initiate appropriate skin toxicity therapy (such as antihistamines, topical corticosteroids and low-dose systemic corticosteroids)
Grade 2	Recommendation: Maintain dose level, but initiate/intensify appropriate skin toxicity therapy (such as antihistamines, topical corticosteroids and low-dose systemic corticosteroids)	Recommendation: Maintain dose level, but initiate/intensify appropriate skin toxicity therapy (such as antihistamines, topical corticosteroids and low-dose systemic corticosteroids)
Grade 3, despite skin toxicity therapy	Recommendation: Hold dose until resolved to Grade ≤ 1, then: If resolved in ≤ 7 days, then reduce dose ↓ 1 dose level If resolved in > 7 days (despite appropriate skin toxicity therapy), then discontinue patient from study drug treatment	Recommendation: Hold dose until resolved to Grade ≤ 1, then: If resolved in ≤ 7 days, then reduce dose ↓ 1 dose level If resolved in > 7 days (despite appropriate skin toxicity therapy), then discontinue patient from study drug treatment
Grade 4, despite skin toxicity therapy	Mandatory: Permanently discontinue patient from study drug treatment.	Mandatory: Permanently discontinue patient from study drug treatment.
General disorders and administration site conditions		
Fatigue/ Asthenia		
Grade 1 or 2	Recommendation: Maintain dose level	Recommendation: Maintain dose level
Grade 3	Recommendation: Hold dose until resolved to ≤ grade 1, then : If resolved in ≤ 7 days, then maintain dose level If resolved in > 7 days, then reduce dose ↓ 1 dose level	Recommendation: Hold dose until resolved to ≤ grade 1, then : If resolved in ≤ 7 days, then maintain dose level If resolved in > 7 days, then reduce dose ↓ 1 dose level
All dose modifications should be based on the worst preceding toxicity.		
^a Common Toxicity Criteria for Adverse Events (CTCAE Version 4.03)		
^b Core LFTs consist of ALT, AST, total bilirubin (fractionated [direct and indirect], if total bilirubin > 2.0 x ULN), and alkaline phosphatase (fractionated [quantification of isoforms], if alkaline phosphatase > 2.0 x ULN.)		
^c “Combined” defined as total bilirubin increase to the defined threshold concurrently with ALT/AST increase to the defined threshold		

Dose modifications for both asciminib and bosutinib		
Please note that if a patient requires a dose interruption of > 28 days for each toxicity, then the patient must be discontinued from the study treatment		
Worst toxicity CTCAE Grade 4.03	Asciminib	Bosutinib

If combined elevations of AST or ALT and total bilirubin do not meet the defined thresholds, please follow the instructions for isolated elevation of total bilirubin and isolated elevation of AST/ALT, and take a conservative action based on the degree of the elevations (e.g. discontinue treatment at the situation when hold dose is needed for one parameter and discontinue treatment is required for another parameter). After all elevations resolve to the defined thresholds that allow treatment re-initiation, re-start the treatment either at the same dose or at one dose lower if meeting a criterion for dose reduction
 
^d “Cholestasis” defined as ALP elevation (>2.0 x ULN and R value <2) in patients without bone metastasis, or elevation of ALP liver fraction in patients with bone metastasis
 
Note: The R value is calculated by dividing the ALT by the ALP, using multiples of the ULN for both values. It denotes whether the relative pattern of ALT and/or ALP elevation is due to cholestatic (R ≤ 2), hepatocellular (R ≥ 5), or mixed (R >2 and < 5) liver injury
 
* Note: If total bilirubin > 3.0 x ULN is due to the indirect (non-conjugated) component only, and hemolysis as the etiology has been ruled out as per institutional guidelines (e.g., review of peripheral blood smear and haptoglobin determination), then ↓ 1 dose level and continue treatment at the discretion of the investigator.
 
** Note: A CT scan or other imaging study to assess the pancreas, liver, and gallbladder must be performed within 1 week of the first occurrence of any ≥ Grade 3 of amylase and/or lipase. If asymptomatic Grade 2 elevations of lipase and/or amylase occur again at the reduced dose, patients will be discontinued permanently from study treatment.
 
*** Note: antidiarrheal medication is recommended at the first sign of abdominal cramping, loose stools or overt diarrhea
		

[figure not shown]

Table 6-3 Dose reduction steps for asciminib and bosutinib

Dose reduction*			
	Starting dose level – 0	Dose level – 1	
Asciminib BID	40 mg tablet BID (total daily dose 80 mg)	20 mg tablet BID (total daily dose 40 mg)	
*Dose reduction should be based on the worst toxicity demonstrated at the last dose.			
Asciminib dose reduction below total daily 40 mg is not allowed. 20 mg tablets will be dispensed to patients in the instance of dose reduction.			
Dose reduction*			
	Starting dose level – 0	Dose level – 1	Dose level – 2
Bosutinib QD	500 mg (1-500 mg tablet QD)	400 mg (4-100 mg tablets QD)	300 mg (3-100 mg tablets QD)
* Dose reduction should be based on the worst toxicity demonstrated at the last dose.			
Bosutinib dose reduction below total daily 300 mg is not allowed. 100 mg tablets will be dispensed to patients in the instance of dose reduction.			

[figure not shown]

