10.4.3 Handling of missing values/censoring/discontinuations

Only patients with MMR at 24 week visit are considered responders. In other words, any patient who achieves MMR before 24 weeks, but is no longer in MMR at 24 weeks, will be considered as a non-responder in this primary analysis. Patients discontinuing the randomized treatment (having performed an EOT visit) prior to 24 weeks due to any reason will be considered as non-responders. One exception to the rule above is if the 24-week PCR evaluation is missing, but both a PCR evaluation at 16 weeks and a PCR evaluation at 36 weeks indicate MMR, the 24-week assessment is imputed as a 'Response'. If PCR evaluations are performed at unscheduled visits closer to the Week 24 visit (before or after), these will be taken into account for the imputation.

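### The Table 6-2 header stops treatment after 28 days' interruption for any toxicity, while Section 6.3.1 and the cytopenia row put the Grade 3/4 cytopenia stop at 42 days, so sites can classify the same patient differently

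*Combined protocol and SAP*

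**What the plan says.** Section 6.3.1 makes the items marked mandatory in Table 6-2 binding on sites. Three statements govern how long a hold may last:

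- **Table 6-2 header, repeated through the table:** "if a patient requires a dose interruption of > 28 days for each toxicity, then the patient must be discontinued from the study treatment". It has no exception for cytopenia.
- **Section 6.3.1 body text:** "If a patient requires a dose interruption of > 28 days for each non-hematologic toxicity, then the patient must be discontinued". The 28 days apply here to non-hematologic toxicity only.
- **Cytopenia rule, in the body text and in the hematologic row:** "If a hematologic toxicity (cytopenia Grade 3 or 4) lasts for more than 42 days without recovery to at least a Grade 2", despite interruption and adequate management, the patient must stop study treatment.

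The Grade 3 and Grade 4 rows for neutropenia and thrombocytopenia each require a hold until Grade 2 or better.

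Section 10.4.3 says that patients who discontinue randomized treatment "prior to 24 weeks due to any reason will be considered as non-responders". Section 10.5.1 derives the Week 96 endpoint in the same way. Section 10.5.2 counts discontinuation for any reason as an event for time to treatment failure (TTF).

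In the same table, the bosutinib cells for isolated AST/ALT elevation at >10-20 and >20 x ULN tell the site to reduce by "1 dose level maintain dose level" when the elevation resolves within 28 days. They label discontinuation after 28 days a recommendation.

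**The concern.** A Grade 3/4 cytopenia triggers a mandatory hold. If it lasts 29 to 42 days, it is an interruption of more than 28 days, so the header requires discontinuation. The body text and the hematologic row do not yet require it. The header appears again above the Grade 3/4 thrombocytopenia rows, where the 42-day sentence is not repeated.

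The choice between these lines can affect the endpoints. A patient stopped on day 29 before Week 24 is a non-responder and a TTF event. A patient with the same course whose site waits for recovery on day 35 remains eligible to respond. The trial is open-label, and Section 1.2.1.2 lists thrombocytopenia and neutropenia among the events seen in more than 10% of patients at 40 mg BID, so such holds are plausible. The effect need not be equal between arms: in the Grade 3/4 rows a bosutinib hold ends only when both neutrophils and platelets have recovered, whereas an asciminib hold looks only at the affected count. Patients are also exposed to inconsistent safety management.

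**Working it through.** **1. The passages side by side, for a Grade 3/4 cytopenia hold**

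| Length of hold | Table 6-2 header | Section 6.3.1 text and hematologic row |
|---|---|---|
| up to 28 days | no stop | no stop |
| 29 to 42 days | must stop | no stop yet |
| more than 42 days, not recovered | must stop | must stop |

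The conflict window is 14 days wide. The two clocks also differ: the header counts days of interruption, the cytopenia rule counts days of cytopenia.

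**2. When it can touch the primary endpoint.** Week 24 is day 24 x 7 = 168. A stop on day 29 of a hold falls before that only if the hold began by about day 168 - 29 = 139, roughly Week 20.

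**3. The plan's own sample size (Section 10.8).** Inputs: 15% against 35%, two-sided 5%, 90% power, 2:1. With pooled variance and no continuity correction:

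- pooled rate = (0.15 + 2 x 0.35)/3 = 0.2833
- n (bosutinib) = [1.960 x sqrt(0.2833 x 0.7167 x 1.5) + 1.282 x sqrt(0.15 x 0.85 + 0.35 x 0.65/2)]² / 0.20² = (1.082 + 0.629)² / 0.04 ≈ 73.2, rounded up to 74
- total = 3 x 74 = 222, as stated; power at 74 and 148 is 90.3%

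Reconciling the time limits leaves these figures as they are.

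**4. Effect of one patient**

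- Would otherwise be in MMR: 1/148 = 0.68 points (asciminib), 1/74 = 1.35 points (bosutinib).
- Would not be in MMR: zero.
- Expected value at the plan's rates: 0.35 x 0.68 = 0.24 points (asciminib), 0.15 x 1.35 = 0.20 points (bosutinib).

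These use the planned arm sizes. The entry for Amendment 03-US.01 reports 233 randomized; at an exact 2:1 split, which is an assumption, the steps are 3/(2 x 233) = 0.64 and 3/233 = 1.29 points.

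**5. Illustration over an assumed range.** The documents give no frequency for holds of 29 to 42 days. Each share below is an assumption.

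| Assumed share of would-be responders lost | Power |
|---|---|
| none | 90.3% |
| 1% in both arms | 89.9% |
| 2% in both arms | 89.5% |
| 5% in both arms | 88.1% |
| 10% in both arms | 85.5% |
| 2% in asciminib only | 88.3% |
| 5% in asciminib only | 84.8% |
| 5% in bosutinib only | 92.7% (a bias towards asciminib, not a gain) |

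A 5% loss in both arms is 148 x 0.35 x 0.05 = 2.6 asciminib and 74 x 0.15 x 0.05 = 0.6 bosutinib responders.

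**6. Whether observed data could settle response.** Table 7-3 schedules PCR up to the end-of-treatment visit. Section 7.1.6 then moves the patient to survival follow-up, which may be by telephone and includes no PCR. The imputation exception in Section 10.4.3 needs PCR results on both sides of Week 24, and none is scheduled after discontinuation.

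**7. Bosutinib AST/ALT cells.** The >10-20 and >20 x ULN cells read as both reduce and maintain. They recommend discontinuation after 28 days, as does the >5-10 x ULN cell. The header and the body text make it obligatory for a non-hematologic toxicity interrupted that long.

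**The case against.** The strongest answer is that the scope is already settled. The body text of Section 6.3.1 names non-hematologic toxicity, and the hematologic row directly under the first header gives the cytopenia limit. The text and the specific row agree; only a general note is unqualified. The 42-day sentence is itself a stop rule and does not order treatment to continue until day 42. The log for Amendment 3 records a change in the cytopenia recovery period from 28 to 42 days, so the header may simply not have been updated. No planned figure is wrong, and no affected patient is known.

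Most of this stands, and it limits the point. A reader might infer that sites are forced to create non-responders. The documents do not support that: a site can follow the body text and the row, and only a site that takes the header literally must stop. What remains is that an unqualified mandatory instruction is repeated through the table, and Section 12 allows no authorized deviations.

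A reader might also see contradictions elsewhere in the table. Two do not hold:

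- **Lipase/amylase.** The Grade 2 row says "Recommendation: Maintain dose level, measure 2x week", and a note says "If asymptomatic Grade 2 elevations of lipase and/or amylase occur again at the reduced dose, patients will be discontinued permanently from study treatment". The note covers a narrower case, recurrence at the reduced dose. It is an exception to the general row.
- **Asciminib AST/ALT.** The threshold for resuming is baseline at >10-20 x ULN and 3 x ULN (5 x ULN for some patients) at >20 x ULN. The bands do not overlap and each gives one instruction. Whether that ordering is sensible is a clinical matter.

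The reduce-and-maintain wording in the bosutinib cells may be a residue of editing or of text extraction. It occurs in both cells, so it should be checked, but it cannot be asserted as an error.

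**Conclusion.** The header disagrees with both the body text of Section 6.3.1 and the hematologic row, in the current text. For cytopenia holds of 29 to 42 days, whether treatment must stop depends on which line the site follows. For holds starting by about day 139, that can decide whether the patient is counted as a non-responder at Week 24.

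The size is unknown, because the number of such holds cannot be derived from the documents. The step of 0.68 or 1.35 points applies only to a patient who would otherwise have been in MMR. It is tempting to say that every discontinued patient moves the rate by that amount, or that the line read by the site always decides response; both overstate. Sample size and planned power are unaffected, and the lower powers in the illustration rest wholly on assumed shares.

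This is an inconsistency worth correcting for safety management and uniform endpoint classification. It does not undermine the primary analysis and is of moderate rather than critical severity. Which limit is clinically right is for the sponsor and its clinical advisers.

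**What to change.** **Protocol.** Reconcile the Table 6-2 header, the body text of Section 6.3.1 and the hematologic row so that each type of toxicity has one stated limit, and say whether the clock counts days of interruption or of toxicity. Check the bosutinib AST/ALT cells at >10-20 and >20 x ULN against the source file, correct them if they do read both ways, and reconcile their recommendation to discontinue after 28 days with the obligation in the header and body text. Tell sites by letter. Recruitment closed on 22-Oct-2019 and the current version is dated 05-Aug-2020, so the last patient's Week 24 (168 days on, about April 2020) has passed. The letter can affect later handling, including Week 96 and patients who switch to asciminib.

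**Analysis.** List by arm the patients discontinued during a cytopenia hold of 29 to 42 days, with their end-of-treatment PCR. If there are any, repeat the Week 24 analysis, and the Week 96 analysis likewise, under two bounds: the listed bosutinib patients counted as responders and the listed asciminib patients as non-responders, then the reverse. Re-analysis on observed Week 24 PCR would be nearly empty, because none is scheduled after the end-of-treatment visit.

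**Cost.** One protocol clarification, one site letter, one flag in the analysis data and one short sensitivity table. No new data are needed.
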